8.1. Serious Adverse Events

8.1.1. Definition of Serious Adverse Event (SAE)

An SAE is any event that meets any of the following criteria at any dose:

- Death
- Life-threatening
- Inpatient hospitalization or prolongation of existing hospitalization
- Persistent or significant disability/incapacity
- Congenital anomaly/birth defect in the offspring of a subject who received rimegepant
- Other Important Medical Events: that may not result in death, be life-threatening, or require hospitalization, may be considered an SAE when, based upon appropriate medical judgment, they may jeopardize the subject and may require medical or surgical intervention to prevent one of the outcomes listed in this definition. Examples of such events are (but not limited to):

- Intensive treatment in an emergency room or at home for allergic bronchospasm
- Blood dyscrasias or convulsions that do not result in inpatient hospitalization
- Development of drug dependency or drug abuse
- Potential drug induced liver injury (see Section 8.4)
- Abuse or Overdose of medication
 - Potential study drug abuse (including cases of repeated excess dosing or subjects who discontinue treatment without returning study drug) should be documented in the source record and reported as an AE or SAE, as appropriate (see Section 7.4). Investigators must monitor subjects for possible cases of abuse of study drug (subjects taking study drug for non-therapeutic purposes, e.g., for psychoactive effects such as high or euphoria). Investigators should obtain more information and explanation from subjects when there are study drug accountability discrepancies.
 - Potential study drug overdose is defined in Section 8.3

In general, hospitalization signifies that the subject has been detained (usually involving at least an overnight stay) at the hospital or emergency ward for observation and/or treatment that would not have been appropriate in the physician's office or outpatient setting. When in doubt as to whether 'hospitalization' occurred or was necessary, the AE should be considered serious.

The following hospitalizations are not considered SAEs in Pfizer clinical studies (but may be considered non-serious AEs):

- A visit to the emergency room or other hospital department <24 hours that does not result in an admission (unless considered “important medical event” or event that is life-threatening);
- Elective surgery planned prior to signing consent;
- Admissions as per protocol for a planned medical/surgical procedure;
- Routine health assessment requiring admission (i.e., routine colonoscopy);
- Admission encountered for another life circumstance that carries no bearing on health and requires no medical intervention (i.e., lack of housing, care-giver respite, family circumstances).

Disability/incapacitating: An AE is incapacitating or disabling if the experience results in a substantial and/or permanent disruption of the subject's ability to carry out normal life functions.

8.1.2. Collection and Reporting Serious Adverse Events

Following the subject's written consent to participate in the study, all SAEs, whether related or not related to study drug, must be collected, including those thought to be associated with protocol-specific procedures. All SAEs must be collected from signing of consent through the 2-week Follow-up Visit. Unresolved SAEs at the time of the 2-week Follow-up Visit should be monitored until resolution of the acute aspects of the safety event, per the opinion of the Investigator. The Investigator should report any SAE occurring beyond the 2-week Follow-up Visit when the event is believed to be related to study drug or other protocol-specific procedures.

All SAEs should be followed to resolution or stabilization.

An SAE report should be completed for any event where doubt exists regarding its status of seriousness.

If the Investigator believes that an SAE is not related to the study drug but is potentially related to the conditions of the study (such as a withdrawal of previous therapy or a complication related to study procedure), the relationship should be specified in the narrative section of the SAE Report.

SAEs, whether related or not related to study drug, overdose (see Section 8.3), potential drug induced liver injury, (see Section 8.4) and pregnancies (see Section 8.5.1) must be reported within 24 hours of the Investigator becoming aware of the event. The Investigator is responsible for submitting all applicable events to the Independent Review Board (IRB) as per the IRB's reporting requirements. Additionally, the Investigator, or designated staff, is responsible for entering the SAE information into the Case Report Form (CRF) and/or system (i.e., event term, start/stop dates, causality, and severity).

Any serious adverse event must be reported immediately or no later than 24 hours after awareness of the event to Pfizer Drug Safety Unit (DSU) either via the Pfizer SAE Submission Assistant (PSSA) tool or using the Pfizer CT SAE report form that must be sent by facsimile (fax) to your country's Pfizer DSU. The CT SAE Report Form should only be used as a backup in the event PSSA is not operational.

If only limited information is initially available, follow-up reports are required. If an ongoing SAE changes in its intensity or relationship to study drug, or if new information becomes available, a follow-up SAE report should be sent within 24 hours of the Investigator becoming aware of the updated information using the same procedure used for the transmission of the initial SAE and the same event term should be used.

The minimum information required for an initial SAE report is:

- Sender of report (Site number, Investigator name)
- Subject identification (subject number)

- Protocol number
- SAE term (if an SAE is being reported)

The Sponsor or specified designee/authorized representative will report suspected unexpected serious adverse reactions (SUSARs) in an expedited manner (without delay) to the Regulatory Authorities and Ethics Committees concerned, in accordance with Food and Drug Administration Code of Federal Regulations (CFR) 21 CFR Parts 312 and 320, Clinical Trials Regulation No 536/2014, and the Detailed Guidance on collection, verification and presentation of adverse reaction reports arising from clinical trials on IPs for human use (ENTR/CT3) and also in accordance with country-specific requirements.

The Sponsor or specified designee/authorized representative shall notify the Investigator of the following information:

Any AE that is both serious and unexpected and is suspected of being related to the use of the IP in this study or in other studies (i.e., SUSAR).

Where required by local legislation, the Investigator shall notify his/her IRB/EC promptly of these new serious and unexpected AE(s) or significant risks to subjects.

8.2. Non-serious Adverse Events

A *non-serious adverse event* is an AE not classified as serious.

8.2.1. Collection and Reporting of Non-serious Adverse Events

The collection of non-serious AE information should begin from signing the ICF through the Follow-up Week 2 Visit.

Non-serious adverse events should be followed until conclusion or stabilization or reported as SAEs if they become serious. Follow-up is also required for non-serious AEs that cause interruption or discontinuation of study drug or those that are present at the end of study treatment.

8.2.2. Laboratory Test Abnormalities

The following laboratory test abnormalities should be captured on the non-serious AE CRF page or SAE Report Form (paper or electronic) as appropriate:

1. Any laboratory test result that is clinically significant or meets the definition of an SAE;
2. Any laboratory abnormality that required the subject to have the study drug discontinued or interrupted;
3. Any laboratory abnormality that required the subject to receive specific corrective therapy.

8.3. Overdose

An overdose is defined as the accidental or intentional administration of any dose of a product that is considered both **excessive** and **medically important**.

There is limited clinical experience with overdose of rimegepant. Treatment of overdose with rimegepant should consist of general supportive measures. There is no known specific antidote for overdose with rimegepant.

Overdose is reportable to Pfizer Safety only when associated with an SAE.

Asymptomatic dosing errors (e.g., accidentally taking multiple tablets instead of the prescribed dose of one tablet in one calendar day) should be reported as deviations.

8.4. Potential Drug Induced Liver Injury (DILI)

Humans exposed to a drug who show no sign of liver injury (as determined by elevations in transaminases) are termed “tolerators,” while those who show transient liver injury but adapt are termed “adaptors.” In some subjects, transaminase elevations are a harbinger of a more serious potential outcome. These subjects fail to adapt and therefore are “susceptible” to progressive and serious liver injury, commonly referred to as DILI. Subjects who experience a transaminase elevation above $3 \times \text{ULN}$ should be monitored more frequently to determine if they are “adaptors” or are “susceptible.”

In the majority of DILI cases, elevations in AST and/or ALT precede T bili elevations ($>2 \times \text{ULN}$) by several days or weeks. The increase in T bili typically occurs while AST/ALT is/are still elevated above $3 \times \text{ULN}$ (ie, AST/ALT and T bili values will be elevated within the same laboratory sample). In rare instances, by the time T bili elevations are detected, AST/ALT values might have decreased. This occurrence is still regarded as a potential DILI. Therefore, abnormal elevations in either AST OR ALT in addition to T bili that meet the criteria outlined below are considered potential DILI (assessed per Hy’s law criteria) cases and should always be considered important medical events, even before all other possible causes of liver injury have been excluded.

The threshold of laboratory abnormalities for a potential DILI case depends on the subject's individual baseline values and underlying conditions. Subjects who present with the following laboratory abnormalities should be evaluated further as potential DILI (Hy's law) cases to definitively determine the etiology of the abnormal laboratory values:

- Subjects with AST/ALT and T bili baseline values within the normal range who subsequently present with AST OR ALT values $\geq 3 \times \text{ULN}$ AND a T bili value $\geq 2 \times \text{ULN}$ with no evidence of hemolysis and an alkaline phosphatase value $< 2 \times \text{ULN}$ or not available.
- For subjects with baseline AST **OR** ALT **OR** T bili values above the ULN, the following threshold values are used in the definition mentioned above, as needed, depending on which values are above the ULN at baseline:
- Preexisting AST or ALT baseline values above the normal range: AST or ALT values ≥ 2 times the baseline values AND $\geq 3 \times \text{ULN}$; or $\geq 8 \times \text{ULN}$ (whichever is smaller).
- Preexisting values of T bili above the normal range: T bili level increased from baseline value by an amount of $\geq 1 \times \text{ULN}$ **or** if the value reaches $\geq 3 \times \text{ULN}$ (whichever is smaller).

Rises in AST/ALT and T bili separated by more than a few weeks should be assessed individually based on clinical judgment; any case where uncertainty remains as to whether it represents a potential Hy's law case should be reviewed with the sponsor. The subject should return to the investigator site and be evaluated as soon as possible, preferably within 48 hours from awareness of the abnormal results. This evaluation should include laboratory tests, detailed history, and physical assessment.

If any potential DILI is identified and meets the criteria above, the Sponsor Medical Monitor (or designee) should immediately be contacted for further instruction on whether the subject must discontinue from the trial and appropriate follow-up requirements. All cases demonstrated on repeat testing as meeting the laboratory criteria of AST/ALT and T bili elevation defined above should be considered potential DILI (Hy's law) cases if no other reason for the LFT abnormalities has yet been found. **Such potential DILI (Hy's law) cases are to be reported as SAEs, irrespective of availability of all the results of the investigations performed to determine etiology of the LFT abnormalities.**

A potential DILI (Hy's law) case becomes a confirmed case only after all results of reasonable investigations have been received and have excluded an alternative etiology.

8.5. Environmental Exposure, Exposure During Pregnancy or Breastfeeding, and Occupational Exposure

Environmental exposure occurs when a person not enrolled in the study as a participant receives unplanned direct contact with or exposure to the study intervention. Such exposure may or may not lead to the occurrence of an AE or SAE. Persons at risk for environmental

exposure include healthcare providers, family members, and others who may be exposed. An environmental exposure may include EDP, EDB, and occupational exposure.

Any such exposures to the study intervention under study are reportable to Pfizer Safety within 24 hours of investigator awareness.

8.5.1. Exposure During Pregnancy

If, following the Baseline Visit it is subsequently discovered that a study subject is pregnant or may have been pregnant at the time of the investigational product exposure, including during at least 6 half-lives after the product administration, the investigational product will be permanently discontinued in an appropriate manner (i.e., dose tapering if necessary for subject safety). Protocol-required procedures for the study discontinued and the follow-up must be performed on the subject unless contraindicated by the pregnancy (i.e., x-ray studies). Other appropriate pregnancy follow-up procedures should be considered if indicated. The investigator must immediately notify the Pfizer (or designee) Medical Monitor and report the event by either using the PSSA tool and by completing an Exposure During Pregnancy (EDP) Supplemental Form following the SAE reporting procedures as described in Section 8.1.2

Follow-up information regarding the course of the pregnancy, including perinatal and neonatal outcome and, where applicable offspring information must be reported on an EDP Supplemental Form.

Any pregnancy that occurs in a female partner of a male study participant should be reported to Pfizer DSU. Information on this pregnancy will be collected on an EDP Supplemental Form, as appropriate.

An EDP occurs if: A female participant is found to be pregnant while receiving or after discontinuing study intervention.

A male participant who is receiving or has discontinued study intervention inseminates a female partner. A female nonparticipant is found to be pregnant while being exposed or having been exposed to study intervention because of environmental exposure. Below are examples of environmental EDP:

A female family member or healthcare provider reports that she is pregnant after having been exposed to the study intervention by ingestion or skin contact.

A male family member or healthcare provider who has been exposed to the study intervention by ingestion or skin contact then inseminates his female partner prior to or around the time of conception.

The investigator must report EDP to Pfizer Safety within 24 hours of the investigator's awareness, irrespective of whether an SAE has occurred. The initial information submitted should include the anticipated date of delivery (see below for information related to termination of pregnancy).

If EDP occurs in a participant/participant's partner, the investigator must report this information to Pfizer Safety using the CT SAE Report Form or via PSSA, regardless of whether an SAE has occurred. Details of the pregnancy will be collected after the start of study intervention and until 66 hours after the last dose.

If EDP occurs in the setting of environmental exposure, the investigator must report information to Pfizer Safety using the CT SAE Report Form or via PSSA. Since the exposure information does not pertain to the participant enrolled in the study, the information is not recorded on a CRF; however, a copy of the completed report is maintained in the investigator site file.

Follow up is conducted to obtain general information on the pregnancy and its outcome for all EDP reports with an unknown outcome. The investigator will follow the pregnancy until completion (or until pregnancy termination) and notify Pfizer Safety of the outcome as a follow up to the initial report. In the case of a live birth, the structural integrity of the neonate can be assessed at the time of birth. In the event of a termination, the reason(s) for termination should be specified and, if clinically possible, the structural integrity of the terminated fetus should be assessed by gross visual inspection (unless pre-procedure test findings are conclusive for a congenital anomaly and the findings are reported).

Abnormal pregnancy outcomes are considered SAEs. If the outcome of the pregnancy meets the criteria for an SAE (ie, ectopic pregnancy, spontaneous abortion, intrauterine fetal demise, neonatal death, or congenital anomaly [in a live born baby, a terminated fetus, an intrauterine fetal demise, or a neonatal death]), the investigator should follow the procedures for reporting SAEs. Additional information about pregnancy outcomes that are reported to Pfizer Safety as SAEs follows:

Spontaneous abortion including miscarriage and missed abortion should be reported as an SAE;

Neonatal deaths that occur within 1 month of birth should be reported, without regard to causality, as SAEs. In addition, infant deaths after 1 month should be reported as SAEs when the investigator assesses the infant death as related or possibly related to exposure to the study intervention.

Additional information regarding the EDP may be requested by the sponsor. Further followup of birth outcomes will be handled on a case by case basis (eg, followup on preterm infants to identify developmental delays). In the case of paternal exposure, the investigator will provide the participant with the Pregnant Partner Release of Information Form to deliver to his partner. The investigator must document in the source documents that the participant was given the Pregnant Partner Release of Information Form to provide to his partner.

8.5.2. Exposure During Breastfeeding

An EDB occurs if: A female participant is found to be breastfeeding while receiving or after discontinuing study intervention.

- A female nonparticipant is found to be breastfeeding while being exposed or having been exposed to study intervention (ie, environmental exposure). An example of environmental EDB is a female family member or healthcare provider who reports that she is breastfeeding after having been exposed to the study intervention by ingestion.

The investigator must report EDB to Pfizer Safety within 24 hours of the investigator's awareness, irrespective of whether an SAE has occurred. The information must be reported using the CT SAE Report Form. When EDB occurs in the setting of environmental exposure, the exposure information does not pertain to the participant enrolled in the study, so the information is not recorded on a CRF. However, a copy of the completed report is maintained in the investigator site file.

An EDB report is not created when a Pfizer drug specifically approved for use in breastfeeding women (eg, vitamins) is administered in accordance with authorized use. However, if the infant experiences an SAE associated with such a drug, the SAE is reported together with the EDB.

8.5.3. Occupational Exposure

The investigator must report any instance of occupational exposure to Pfizer Safety within 24 hours of the investigator's awareness using the CT SAE Report Form or PSSA, regardless of whether there is an associated SAE. Since the information about the occupational exposure does not pertain to a participant enrolled in the study, the information is not recorded on a CRF; however, a copy of the completed report is maintained in the investigator site file.

8.6. Lack of Efficacy

The investigator must report signs, symptoms, and/or clinical sequelae resulting from lack of efficacy. Lack of efficacy or failure of expected pharmacological action is reportable to Pfizer Safety **only if associated with an SAE**.

8.7. Medication Errors

Medication errors may result from the administration or consumption of the study intervention by the wrong participant, or at the wrong time, or at the wrong dosage strength. Medication errors are recorded and reported as follows:

Recorded on the Adverse Event Page of the CRF	Reported on the CT SAE Report Form or PSSA to Pfizer Safety Within 24 Hours of Awareness
All medication errors (regardless of whether associated with an AE). Any AE or SAE associated with the medication error	Only if associated with an SAE

Medication errors include:

- Medication errors involving subject exposure to the study drug;
- Potential medication errors or uses outside of what is foreseen in the protocol that do or do not involve the study subject.
- The administration of expired study drug;
- The administration of an incorrect study drug;
- The administration of an incorrect dosage:
 - Subjects taking > 2 tablets in one calendar day
 - Subjects who have < 80% study drug compliance between visits
- The administration of study drug that has undergone temperature excursion from the specified storage range, unless it is determined by the sponsor that the study drug under question is acceptable for use.

If applicable, any associated serious and nonserious AE(s) are recorded on the AE page of the CRF.

In the event of a medication dosing error, the sponsor should be notified within 24 hours. Medication errors should be reported to Pfizer Safety within 24 hours via PSSA **only when associated with an SAE**.

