7.4. Treatment Compliance

Responsible study personnel will dispense the study drug. Subjects are required to finish a wallet of study drug before starting a new wallet. Accountability and compliance verification should be documented in the subject's study records.

Subjects must be counseled on the importance of taking the study drug as directed (see Section 7.2.2). Treatment compliance and review of study drug doses through review of returned study drug should be assessed by site staff at each study visit. Discrepancies between review of study drug and information provided by subject must be documented in the source record. Investigators should inform subjects that involuntary termination from the study will occur in cases where non-compliance is identified. Study staff should contact a subject between the monthly study visits if the subject demonstrates non-compliance with the

eDiary and document the contact in the source, to identify potential lost to follow-up subjects as early as possible.

Investigators must monitor subjects for possible cases of abuse of study drug (subjects taking study drug for non-therapeutic purposes, e.g., for psychoactive effects such as high or euphoria). Investigators should also assess study drug accountability discrepancies (e.g., missing study drug, loss of medication, or non-compliance cases in which more study drug was used, as compared to expected). Investigators should obtain more information and explanation from subjects when there are study drug accountability discrepancies (see Section 8.1.1).

Cases of study drug non-adherence, including subjects who discontinue treatment without returning study drug, should be reported as protocol deviations.

All cases of treatment non-compliance, during the DBT Phase, are to be discussed with the Sponsor, and corrective training is to be completed and documented, prior to the subjects enrollments into the OLE Phase.

Cases of excess dosing (e.g., taking >1 tablet of study drug every other day) should be reported as protocol deviations. In the event that an occurrence(s) of excess dosing is believed, in the opinion of the Principal Investigator, to have possibly caused or exacerbated a clinically-significant adverse outcome or serious adverse outcome, the AE resulting from the excess dosing should be reported as aSAE.

Dosing errors not associated with a SAE (e.g., accidentally taking 2 tablets EOD) need only be reported as deviations.

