### **Data Sources for Endpoints**

Migraine days, acute migraine-specific medication days, acute migraine medication days, headache days, MFIQ scores, and PGA – Migraine scores during the DBT Phase are derived from electronic diary (eDiary) data from the external source YPrime. Acute migraine-specific medications are triptans, ergotamine, lasmiditan, or ubrogepant. Acute migraine medications are acute migraine-specific medications and other protocol-allowed medications to treat headache (migraine or nonmigraine) or aura taken on a migraine day.

AEs are determined from AE CRFs.

Grade 3 to 4 laboratory test abnormalities are determined from laboratory test values graded using standardized criteria (see Section 6.4.2 for more details). Laboratory test results are from an external central laboratory and local laboratory test CRFs.

Endpoints based on other rating scale and questionnaires (i.e., C-SSRS, HIT-6, MIBS, MSQ, WPAI – Migraine, PGA – Migraine during the OLE Phase) are derived from their respective CRFs.

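### Protocol 8.7 puts dosing errors without a clinical event on the AE page while 7.4 and 8.3 treat them as deviations, so AE tables may include adherence records

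*Protocol*

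**What the plan says.** Protocol 8.7 has a two-column table. The column for the AE page of the CRF begins "All medication errors (regardless of whether associated with an AE", so the record does not depend on a clinical event. Under incorrect dosage the section names two cases: "Subjects taking > 2 tablets in one calendar day" and "Subjects who have < 80% study drug compliance between visits". The list is introduced as examples and has a general item, "Potential medication errors or uses outside of what is foreseen in the protocol that do or do not involve the study subject".

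Protocol 7.4 directs the same kinds of event elsewhere. On adherence: "Cases of study drug non-adherence, including subjects who discontinue treatment without returning study drug, should be reported as protocol deviations". On dosing errors: "Dosing errors not associated with a SAE (e.g., accidentally taking 2 tablets EOD) need only be reported as deviations". Its response to compliance below 80% is re-education at dispensation visits; the AE page is not mentioned. Protocol 8.3 also makes asymptomatic errors involving several tablets a deviation.

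Protocol 8.1.1, under potential study drug abuse, says that "subjects who discontinue treatment without returning study drug) should be documented in the source record and reported as an AE or SAE, as appropriate".

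In the SAP, the data-source text in Section 3.2 says "AEs are determined from AE CRFs". SAP 6.4.1.2 to 6.4.1.4 then tabulate any AE, AEs by system organ class and preferred term, and potential drug abuse AEs. SAP 6.2.6.2 and 9.1 separately derive more than one tablet on any day, and tablet-count compliance against 80%, from the dosing CRFs.

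**The concern.** AE frequency by intensity is other secondary endpoint 1 (Protocol 3.2.2) and carries the tolerability conclusion of the study. Protocol 8 defines an AE as an untoward medical occurrence. A missed tablet on its own is not one, yet 8.7 places it on the page from which the SAP draws AEs.

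The instructions in 8.7 and in 7.4/8.3 cannot both govern the same event. Recording every medication error on the AE page is incompatible with saying that errors without an SAE need be reported only as deviations. A site that follows Section 7.4 enters nothing on the AE page; a site that follows 8.7 enters a record. If those records are counted, the any-AE percentage partly measures adherence and which section a site happened to read. The potential-abuse row raises a smaller version of the same question, if unreturned drug with no sign of misuse is entered there.

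The thresholds also disagree. The over-dosing example in 8.7 starts above two tablets in a day. Protocol 1.3.1 and 7.2.2 allow one tablet per dosing day, and the SAP flags more than one.

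**Working it through.** **Sections side by side**

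| Event, no clinical consequence | Protocol 8.7 | Protocol 7.4 / 8.3 | SAP |
|---|---|---|---|
| Compliance <80% between visits | Named; AE page | Deviation; re-education | 9.1: <80% over the whole phase is a relevant deviation |
| Exactly 2 tablets in a day | Below the named >2 threshold; a general item could cover it | Deviation only | 6.2.6.2 and 9.1: >1 tablet flagged |
| 3 or more tablets in a day | Named; AE page | Deviation | Flagged |
| Drug not returned after discontinuation | Not named | Deviation (7.4); AE or SAE as appropriate under potential abuse (8.1.1) | Potential drug abuse AE row |

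**How few missed doses reach 80%**

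The plan's own 80% figure reproduces. SAP 6.2.6.2 equates 80% of every-other-day dosing with 11.2 tablets per 28-day month: 28/2 = 14 doses, and 0.80 × 14 = 11.2.

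The same section defines required exposure over n days as integer((n + 1)/2).

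- 14-day interval (Baseline to Week 2, Week 2 to Week 4): integer(15/2) = 7 doses. One missed: 6/7 = 85.7%. Two missed: 5/7 = 71.4%, below 80%.
- 28-day interval: integer(29/2) = 14 doses. Two missed: 12/14 = 85.7%. Three missed: 11/14 = 78.6%, below 80%.
- Protocol Table 1 puts Week 12 at Day 86, 29 days after Day 57. That interval could hold integer(30/2) = 15 doses; three missed is then exactly 80%, and four are needed (11/15 = 73.3%).

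**Sensitivity under assumed missed-dose rates**

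The documents give no missed-dose rate. The rates below, and independence between doses, are assumptions. Let a = P(at least 2 of 7 missed) and b = P(at least 3 of 14 missed).

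- Scheduled visits taken as 7, 7, 14 and 14 doses: P(any interval <80%) = 1 − (1 − a)²(1 − b)².
- Dispensing intervals only, 3 × 14 doses: P = 1 − (1 − b)³.

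| Missed-dose rate | a | b | 7, 7, 14, 14: P; of 600 | 3 × 14: of 600 |
|---|---|---|---|---|
| 2% | 0.0079 | 0.0025 | 2.1%; 12 | 4 |
| 3% | 0.0171 | 0.0077 | 4.9%; 29 | 14 |
| 5% | 0.0444 | 0.0301 | 14.1%; 85 | 52 |
| 10% | 0.1497 | 0.1584 | 48.8%; 293 | 242 |

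The range is too wide to serve as an estimate. It shows only that the 8.7 criterion can be met often at modest rates of non-adherence, and that the count depends on whether Week 2, which is not a dispensing visit, closes an interval.

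**The case against.** The strongest objection is that an entry on the AE page is not the same as being counted as an AE. Protocol 8.7 itself separates a medication error from any AE associated with it, terms are coded and so identifiable, and SAP 6.4.1 leaves counting rules and table contents to the Core SAP. That document may already remove such records. This stands: the effect on the tables is an inference from the SAP text, which states no exclusion. A reader might infer that AE counts will include these records, or that unreturned drug will appear in the potential-abuse row. The documents do not establish either, and the SAP does not itself define a potential drug abuse AE.

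A reader might also infer that double doses go unrecorded. They do not. The 8.7 list is not exhaustive, 7.4 and 8.3 make a double dose a deviation, and the SAP flags more than one tablet on any day. Only the named threshold in 8.7 leaves out exactly two tablets.

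Nor do 8.1.1 and 7.4 strictly contradict each other on unreturned drug. Section 8.1.1 concerns potential abuse and reporting as appropriate, 7.4 does not say deviation only, and one event can be reported both ways. What is missing is a statement of when the AE report applies.

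Finally, the sponsor hears of dosing errors within 24 hours (8.7) and discusses DBT non-compliance with sites (7.4), which may even out practice. The same rules apply in both blinded arms, and nothing here points to a bias between arms. Both points limit the consequence. Neither resolves the conflict between 8.7 and 7.4/8.3.

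**Conclusion.** The inconsistency is real and lies in the protocol text. Section 8.7 sends dosing errors and low between-visit compliance to the AE page without requiring a clinical event, while 7.4 and 8.3 handle them as deviations. Sites can comply and still differ.

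The consequence is conditional. The tables for other secondary endpoint 1 may include non-clinical adherence records, because the SAP takes AEs from the AE CRFs and states no exclusion; the Core SAP, not seen here, could settle it. The size cannot be computed from the documents. The firm figures are the triggers: two missed doses of 7, or three of 14. The plausible harm is AE percentages that are raised and dependent on site practice, not a distorted comparison between arms. The point is worth correcting because it affects the meaning of a stated endpoint and costs little to settle.

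**What to change.** 1. Reconcile Protocol 7.4, 8.3 and 8.7 on whether dosing errors and <80% compliance without a clinical event go on the AE page or are deviations only. In the same step, reconcile the wording in 8.7 about more than two tablets with the one-tablet limit elsewhere in the protocol and the >1 tablet flag in the SAP. The sponsor should decide which rule and threshold apply; this review does not choose between them.
2. Clarify in 8.1.1 and 7.4 when unreturned drug is reported as potential abuse in addition to being a deviation.
3. Add to SAP 6.4.1 that AE-page medication-error records with no associated clinical event are excluded from the AE frequency tables and listed separately, or cite the Core SAP rule that does this. The SAP sentence would also cover entries already made.

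The cost is a protocol clarification, one SAP sentence, one extra listing and a check of existing AE-page entries.
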